8.2 Data Review Committee

8.2.1 Cohort A - Safety Run-In

Pembrolizumab has not previously been combined with bemcentinib in patients (in any indication) and therefore a safety run-in will include a total of 12 patients.

A Data Review Committee (DRC), consisting of Principal Investigators, the Sponsors' (BerGenBio and Merck) medical monitors, and invited experts as required e.g., statistician, PK or PD specialist, will review all patient safety data after 6 patients have been enrolled and followed up for 6 weeks (2 cycles) and then again after a further 6 patients (total 12 patients) have had the potential for 6 weeks follow-up. At each of these safety reviews, the DRC will consider the rate of bemcentinib dose reductions and the rate of permanent discontinuation from bemcentinib and pembrolizumab.

Each patient will have had the potential to receive (as a minimum):

- 2 cycles of pembrolizumab.
- Bemcentinib at [REDACTED] for 3 days, followed by [REDACTED] daily for ~6 weeks.

At the 1st safety run-in (based on 6 patients) the DRC will evaluate the need for dose modification for individual patients, or bemcentinib loading or daily dose modification. A rate of >66% (4 or more) of patients requiring treatment to be dose reduced (bemcentinib) or permanently discontinued (either bemcentinib or pembrolizumab, or both) will be considered as a significant rate.

The 2nd safety run-in (based on the 12 patients) the DRC will again evaluate the need for dose modification for individual patients, or bemcentinib loading or daily dose modification. A rate of >40% (5 or more) of patients requiring treatment to be dose reduced (bemcentinib) or permanently discontinued (either bemcentinib or pembrolizumab, or both) will be considered as a significant rate.

During the safety run-in reviews, the DRC will have the option to recommend a lower dose of bemcentinib (dose level -1) for new patients. Dose level -1 is defined as [REDACTED] bemcentinib on Days 1, 2 and 3 followed by [REDACTED] from Day 4 onwards.

Additionally, a review of emerging safety data from the whole bemcentinib program will be made 6 monthly.

8.2.2 Cohort A - End of Stage 1 – Efficacy Analysis

Recruitment for Cohort A will be halted after 22 evaluable patients have been entered, and whilst the interim (Stage 1) analysis is conducted. Recruitment will recommence if the decision is made to continue to the maximum of 48 (EE) evaluable patients.

BerGenBio ASA
[name]
[name]
Norway

The DRC will meet to review the overall risk / benefit profile of the combination, together with the ORR when 22 patients have been followed up for at least 24 months – and therefore, will have data from at least 2 post-treatment tumor assessment scans. The DRC will document the ORR, and if it favors the null hypothesis for futility, will recommend if the study should proceed to evaluate up to a further 26 patients. This recommendation will take into account the statistically driven endpoint, in the context of on-going safety data review of the combination approach, as well as the quality of the response e.g., available data on DoR and PFS, where possible.

Appropriate representatives of the Sponsor and the coordinating personnel may also attend and minute DRC meetings. Recommendations of the DRC will be documented and sent to the sites. Further details on the composition of the DRC, as well as the process for data review, issue of recommendations and decision making, are described in a separate DRC charter for this study.

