3.5 Definition of Evaluable Patient, Acceptable Compliance, and Replacement of Patients

Evaluable for safety (ES): An evaluable patient will have received at least one combination dose.

Evaluable for efficacy (EE): An evaluable for safety patient who has at least one on-treatment scan per protocol schedule.

Patients will be replaced if they are considered to be non-evaluable for efficacy.

Patients who have failed screening (usually because they have failed one or more of the inclusion or exclusion criteria) will not receive study treatment and are not considered evaluable.

Treatment non-compliance for this study will be defined as follows:

- For bemcentinib: missing more than 7 doses in any 21-day period (other than a dose delay for toxicity management ([Section 6.6.1](#)))
- For pembrolizumab: Dosing interruptions are permitted in the case of medical / surgical events or logistical reasons not related to study therapy (for example, elective surgery, unrelated medical events, patient vacation etc). Patients should be placed back on study therapy within 3 weeks of the scheduled interruption. The reason for the interruption should be documented in the patient's study notes.

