4 STUDY DESIGN

This is an open-label, multi-center, single arm, phase II study to assess the anti-tumor activity and safety of bemcentinib in combination with pembrolizumab in patients with previously treated advanced adenocarcinoma of the lung.

The study will enroll three cohorts of patients with previously treated, advanced adenocarcinoma of the lung: Cohort A will consist of patients who received a maximum of one prior line of platinum-containing chemotherapy and no prior immunotherapy of any kind. Cohort B will consist of patients with a maximum of one prior line of an anti-PD-(L)1 therapy (monotherapy). Cohort C will consist of patients who received a maximum of one prior line of therapy with an anti-PD-(L)1 therapy in combination with a platinum-containing chemotherapy.

Cohort A will utilize a 2-stage, single-arm design, Simon's 2-stage design¹ with a single interim (Stage 1) analysis and a final (Stage 2) analysis. The interim (Stage 1) analysis will be conducted for the Data Review Committee (DRC) when 22 patients are evaluable (EE) for Objective Response Rate (ORR). If 3 or fewer responses are observed in up to 22 (EE) patients, the cohort will be terminated in favor of the null hypothesis for futility, and no further participants will be recruited. When at least 4 patients have an observed response at the interim analysis, up to a further 26 patients may be evaluated (EE), for a total of 48 evaluable (EE) patients (see [Section 8.1](#)), taking the overall risk benefit of the combination into account.

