4.1 Cohort A - Safety Run-In

Pembrolizumab has not previously been combined with bemcentinib in patients (in any indication) and therefore, a safety run-in will include a total of 12 patients. The internal DRC will conduct a review of the safety data from the first 6 patients who have had the potential to be followed for at least 6 weeks (minimum 2 cycles), and then again after a further 6 patients (12 patients in total) have had the potential to be followed for at least 6 weeks. At each of these safety reviews, the DRC will consider the rate of bemcentinib dose reductions and the rate of permanent discontinuation from bemcentinib and pembrolizumab.

The DRC will consider whether to recommend a lower dose of bemcentinib (dose level -1) for new patients. Dose level -1 is defined as [REDACTED] bemcentinib on Days 1, 2 & 3, followed by [REDACTED] from Day 4 onwards.

For the safety run-in reviews, each patient will have had the potential to receive (as a minimum):

- 2 cycles of pembrolizumab.
- Bemcentinib at [REDACTED] for 3 days, followed by [REDACTED] daily for ~ 6 weeks.

The DRC will consist of Principal Investigators, the Sponsors' (BerGenBio and Merck) medical monitors, and invited experts as required, will review all patient safety data, including SAEs, AEs, laboratory and ECG results, dosing information, including dose reductions and permanent discontinuations.

4.2 End of Stage 1 – Efficacy Analysis and Review of Emerging Risk-Benefit Profile

For cohort A, the DRC will meet to review the ORR after 22 patients have been followed up for at least 24 weeks. The DRC will document the ORR and, if it favors the null hypothesis for futility, will recommend if the study should proceed to evaluate up to a further 26 patients. For cohort B, after 1 response has been confirmed, a subgroup of the DRC will meet to confirm continuation to Stage 2 and evaluation of 16 further patients. An interim analysis (for Stage 1) will be conducted

BerGenBio ASA
[name]
[name]
Norway

[figure not shown]

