8 DATA EVALUATION: CRITERIA FOR EVALUATION OF OBJECTIVES

8.1 Statistical Considerations, Interim Analysis and Sample Size

The study will employ a k -stage single-arm design, an approach derived from basic statistical theory²⁸. For cohort A, if p denotes the true tumor response rate with drug, the null and alternative hypotheses to be assessed in this trial are: $H_0: RR=p_0$ vs $H_1: RR=p_1$ ($p_0 < p_1$), with $p_0=0.15$ and $p_1=0.30$. To test these hypotheses, this trial is a k -stage single-arm design with $k=2$, being a Simon's 2-stage design¹. In this design with $k=2$, there are two analyses: a single interim (Stage 1) and a final (Stage 2) analysis. At the interim analysis, the response rate is evaluated in a fixed number (m) of patients using a predefined decision rule to determine if the study should stop for futility. If the study is not stopped for futility, a further fixed number of patients (l) are assessed for response, and a final analysis is performed on all ($m+l$) patients. In both interim and final analyses, the response rate will be presented together with the associated exact 90% CI.

With $p_0=0.15$ and $p_1=0.30$, the interim (Stage 1) analysis will be conducted with $m=22$ for efficacy patients (EE). If 3 or fewer responses are observed in these 22 patients, the cohort will be terminated in favor of the null for futility. Otherwise, a further 26 patients may be evaluated, for a total of 48 evaluable patients. If a total of 12 or more responses are seen in 48 evaluable patients (25%), then the null will have been rejected in favor of the alternative; otherwise, the null will not have been rejected.

Based on 500,000 trial simulations, this design provides an overall power of 80.1% to test the stated null and alternative hypothesis with a 1-sided Type I error rate of 0.049. Under the null, the probability of correctly stopping for futility at Stage 1 is 57.7%.

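### Cohort A Stage 1 review is timed at 24 months in Section 8.2.2 but 24 weeks in Section 4.2, and both sections give the DRC discretion where the futility rule requires a stop

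*Combined protocol and SAP*

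**What the plan says.** **Timing.** Section 8.2.2, the section devoted to this decision, has the DRC review risk-benefit "together with the ORR when 22 patients have been followed up for at least 24 months", and adds that this follow-up will supply at least two post-treatment tumor scans. Section 4.2 says of the same meeting that the DRC will "review the ORR after 22 patients have been followed up for at least 24 weeks". The synopsis and Section 4 give no follow-up period. They place the analysis at the point when 22 patients are evaluable for efficacy (EE), which Section 3.5 defines as "An evaluable for safety patient who has at least one on-treatment scan per protocol schedule".

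**Recruitment.** Section 8.2.2 states: "Recruitment for Cohort A will be halted after 22 evaluable patients have been entered, and whilst the interim (Stage 1) analysis is conducted". The synopsis says the same.

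**Decision rule.** Section 8.1 states: "If 3 or fewer responses are observed in these 22 patients, the cohort will be terminated in favor of the null for futility". The synopsis and Section 4 repeat the rule, add that nobody further is recruited, and bring in risk-benefit only once at least 4 patients have responded. Section 8.2.2 instead says the DRC will document the response rate and, "if it favors the null hypothesis for futility, will recommend if the study should proceed to evaluate up to a further 26 patients". Section 4.2 carries almost the same sentence.

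**The concern.** This is the only futility look in cohort A, and the protocol contradicts itself on when it happens and on what follows from the result.

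On timing, the choice between weeks and months fixes how long recruitment stays closed. The trigger of 22 EE patients is looser again, because one scan is enough for EE status. Response should be confirmed by a repeat scan at least 4 weeks later (synopsis, Sections 8.5 and 8.11), so a look after one scan could undercount responders against the boundary of 3.

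On the decision, the DRC sentence attaches discretion to the wrong outcome. Read literally, it lets the DRC continue when the result favours the null, where Section 8.1 allows no continuation. It says nothing about 4 or more responses, which is where the synopsis places the discretion. If the stop is only advisory, the stated 57.7% chance of stopping early under the null is not a property of the design.

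**Working it through.** **Inputs.** Section 8.1: p0 = 0.15, p1 = 0.30; stop at 3 or fewer responses in 22; reject the null at 12 or more in 48; stated power 80.1%, one-sided Type I error 0.049, and 57.7% probability of a futility stop under the null. Section 5.1.1: scans at weeks 10, 19, 28, 37, 46, 58, 70, 82, 94, 106.

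**1. The plan's own stopping probability.** With X ~ Binomial(22, 0.15):

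P(X ≤ 3) = 0.0280 + 0.1087 + 0.2015 + 0.2370 = 0.575.

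This agrees with the stated 57.7% to within 0.2 percentage points. The stated figure therefore assumes that every result of 3 or fewer leads to a stop.

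**2. Operating characteristics, stop binding or not.**

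- Binding: P(reject) = Σ from x = 4 to 22 of P(X = x) × P(Y ≥ 12 − x), with Y ~ Binomial(26, p).
- Always overridden: P(reject) = P(Z ≥ 12), with Z ~ Binomial(48, p).
- Overridden only at exactly 3 responses: the binding formula with the sum starting at x = 3.
- Expected N under p0 = 22 + 26 × (1 − stopping probability).

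| DRC behaviour at 3 or fewer | Stop probability, p = 0.15 | Type I error | Power, p = 0.30 | Expected N, p = 0.15 |
|---|---|---|---|---|
| Always stops (Section 8.1) | 57.5% | 0.0446 | 79.7% | 22 + 26 × 0.425 = 33.0 |
| Continues only at exactly 3 | 33.8% | 0.0471 | 81.4% | 22 + 26 × 0.662 = 39.2 |
| Always continues | 0% | 0.0478 | 81.9% | 48 |

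The exact power of 79.7% is close to the stated 80.1%. The exact Type I error of 0.0446 is below the stated 0.049. That discrepancy is a separate matter and is in the conservative direction.

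**3. Scans available at each timing.**

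- By week 24: weeks 10 and 19, so 2 scans.
- By 24 calendar months (24 × 365.25 / 12 / 7 = 104.4 weeks): weeks 10 to 94, so 9 scans, with a tenth scheduled at week 106.

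The two-scan explanation in Section 8.2.2 matches 24 weeks. Two further passages point the same way: Section 8.1 and the synopsis use 24 weeks in the Stage 1 rule for cohorts B and C, and Section 8.3 uses 24 months for the cohort A final analysis.

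**4. Length of the halt.** The difference is 104.4 − 24 = about 80 weeks. With the 4-week months of the Table 3 footnote it is 96 − 24 = 72 weeks. If the halt starts only when the 22nd patient has had the week 10 scan, its minimum length is 24 − 10 = 14 weeks under Section 4.2 and about 104 − 10 = 94 weeks under Section 8.2.2, so the difference is unchanged.

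**The case against.** The best answer on timing is that 24 months is an evident slip of unit which the document corrects itself. The two-scan explanation, Section 4.2 and the 24-week wording for the other cohorts all point to weeks, so a two-year halt is unlikely in practice. The EE trigger can also be read as saying who is counted, with 24 weeks saying how long they are followed. Both points are fair. They make the intended meaning fairly clear, but nothing in the protocol says which section prevails, and the erroneous figure sits in the section that governs the decision.

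On the DRC sentence, the termination rule is stated firmly in the synopsis, Section 4 and Section 8.1. The DRC only recommends, Section 8.2.2 says it will take the statistical endpoint into account, and the DRC charter may settle the matter. An inverted condition is a plausible explanation. However, the sentence appears in two sections, Section 8.2.2 goes on to list what the recommendation weighs (safety, duration of response, PFS), and Section 8.6 also describes early termination as something the DRC recommends. The charter is not among the documents and cannot be assumed to resolve the conflict.

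It is also true that 0% is a worst case, that power rises slightly when the stop is overridden, and that Type I error stays under 5%. All of that stands, and it limits the harm to accrual time and patient numbers.

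**Conclusion.** The concern holds on both points. The review has two incompatible follow-up times, about 80 weeks apart, and the protocol's own scan count supports 24 weeks. The DRC instruction in Sections 4.2 and 8.2.2 contradicts the mandatory stop in the synopsis and Sections 4 and 8.1. The stated 57.7% chance of stopping under the null is delivered only if the stop binds; otherwise it can fall as far as 0%, with up to 15 more patients expected under the null (48 − 33.0).

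The validity of the final test is not threatened: Type I error lies between 0.0446 and 0.0478 however the DRC acts at 3 or fewer responses. These figures assume independent responses with a common probability, exactly 22 and 48 evaluable patients, and the 12-of-48 rejection rule. This must be corrected because it concerns the timing and direction of the cohort's only futility decision.

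**What to change.** 1. In Section 8.2.2, change 24 months to 24 weeks.
2. Use the same trigger in the synopsis and Sections 4, 4.2 and 8.1: 22 EE patients, each followed for at least 24 weeks.
3. In Sections 4.2 and 8.2.2, replace the DRC sentence with: *If 3 or fewer of the 22 evaluable patients respond, the cohort stops. If 4 or more respond, the DRC recommends whether to proceed to up to 26 further patients, considering overall risk-benefit.* Align Section 8.6 with this.
4. Check the DRC charter against the corrected text.
5. If the Stage 1 review has already taken place, record which follow-up time and which decision rule were applied.

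If the sponsor in fact wants an advisory stop, Section 8.1 should say so, drop the 57.7% as a guaranteed figure, and report the non-binding values (Type I error up to 0.0478, power up to 81.9%, sample size up to 48).

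The cost is a protocol amendment: one word in Section 8.2.2, one sentence replaced in each of two sections, short wording changes elsewhere for consistency, and a charter check. No extra patients or assessments are needed.

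### Sections 4.2 and 8.2.2 tie the DRC's recommendation on whether to proceed in cohort A to a result that favors the null, which contradicts the mandatory futility stop in Section 8.1

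*Combined protocol and SAP*

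**What the plan says.** Section 8.1 sets the cohort A rule: "If 3 or fewer responses are observed in these 22 patients, the cohort will be terminated in favor of the null for futility". It goes on: "Otherwise, a further 26 patients may be evaluated, for a total of 48 evaluable patients". The synopsis and Section 4 give the same threshold in equally mandatory terms. Both the synopsis design text and Section 4 add that recruitment then ends, and that continuation after at least 4 responses takes the overall risk-benefit into account.

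Section 8.1 also states the operating characteristics, based on 500,000 simulations: "this design provides an overall power of 80.1" per cent, "with a 1-sided Type I error rate of 0.049", and "Under the null, the probability of correctly stopping for futility at Stage 1 is 57.7" per cent.

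Sections 4.2 and 8.2.2 describe the DRC's Stage 1 meeting. In both, the committee's task once the response rate is recorded reads: "if it favors the null hypothesis for futility, will recommend if the study should proceed to evaluate up to a further 26 patients". Section 8.2.2 adds that the recommendation weighs the response result together with safety and, where available, DoR and PFS.

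**The concern.** The condition in Sections 4.2 and 8.2.2 points the wrong way. Under Section 8.1, 3 responses in 22 ends the cohort. Under Section 8.2.2, the same 3 responses lead to a DRC recommendation on whether to enrol 26 more patients, on grounds that go beyond the response count. Nothing in the protocol calls the boundary non-binding or says which text prevails.

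This is the only go/no-go rule on the primary endpoint before Stage 2, in an open-label trial. The DRC consists of Principal Investigators, the sponsors' medical monitors and invited experts as required. If the cohort continued after 3 of 22, a reader of the final report could not tell whether the plan had been followed or departed from. The early-stopping probability, which is the main reason for a two-stage design, would no longer be assured.

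**Working it through.** **Inputs (all Section 8.1, cohort A).** Null rate 0.15, alternative 0.30; Stage 1 size 22; stop at 3 or fewer; Stage 2 adds 26 for a total of 48; reject the null at 12 or more ("If a total of 12 or more responses are seen in 48 evaluable patients").

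**Step 1: reproduce the stated figures with the stop followed (exact binomial).**

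Stopping probability under the null = P(X ≤ 3 | n = 22, p = 0.15) = 0.0280 + 0.1087 + 0.2015 + 0.2370 = 0.575.

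Expected N under the null = 22 + 26 × (1 − 0.575) = 33.0.

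Rejection probability = sum over x = 4 to 22 of P(X₁ = x) × P(X₂ ≥ 12 − x | n = 26, p). This gives 0.0446 at p = 0.15 and 0.797 at p = 0.30.

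| Quantity | Stated | Exact |
|---|---|---|
| Stopping probability under the null | 57.7% | 57.5% |
| Power | 80.1% | 79.7% |
| One-sided type I error | 0.049 | 0.0446 |

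The stopping probability and power agree closely. The stated type I error is higher than the exact value; that is a separate matter and does not affect this point. The stated stopping probability is therefore that of a stop that is always followed.

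**Step 2: allow continuation after 3 or fewer responses.** The documents give no rate at which this would happen, so let q be an assumed share of boundary-met cases in which the cohort continues, the same for every count from 0 to 3. Then:

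- stopping probability = 0.575 × (1 − q)
- expected N = 48 − 26 × 0.575 × (1 − q)
- rejection probability lies on a straight line between the two-stage value (q = 0) and P(X ≥ 12 | n = 48, p) (q = 1)

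| q | Stopping probability, p = 0.15 | Expected N, p = 0.15 | Type I error | Power |
|---|---|---|---|---|
| 0 | 57.5% | 33.0 | 0.0446 | 79.7% |
| 0.25 | 43.1% | 36.8 | 0.0454 | 80.2% |
| 0.50 | 28.8% | 40.5 | 0.0462 | 80.8% |
| 0.75 | 14.4% | 44.3 | 0.0470 | 81.3% |
| 1 | 0% | 48.0 | 0.0478 | 81.9% |

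If the cohort continues only at exactly 3 responses, the stopping probability is 0.575 − 0.237 = 33.8% and type I error is 0.0471.

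**Step 3: the worst case in patients.** The average excess when the boundary is always overridden is 26 × P(X ≤ 3 | n = 22, p):

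- true ORR 15%: 26 × 0.575 = 15.0 patients
- true ORR 10%: 26 × 0.828 = 21.5 patients

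**The case against.** The strongest reply is that this is a drafting slip whose intent is plain. The stop is mandatory in the synopsis, Section 4 and Section 8.1, and the section that carries the operating characteristics is unambiguous. I agree that a dropped 'not' is the likeliest explanation. It does not remove the problem: the clause appears in two operative sections, and those are the sections that tell the DRC how to run the Stage 1 review. Section 8.2.2 refers process details to a DRC charter, which is not among the documents, so it cannot be shown to settle the matter either way.

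Four stronger readings are tempting and are not supported.

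- *That the DRC decides.* Both sections say it recommends. Section 8.2.2 mentions a decision to continue without saying who takes it.
- *That no DRC role is described once the boundary is passed.* The synopsis and Section 4 make continuation after at least 4 responses subject to risk-benefit. Section 8.2.2 opens with a DRC review of risk-benefit and ORR that has no such condition. Section 8.6 allows a DRC recommendation of early termination after the Stage 1 review. The gap is confined to the conditional sentence.
- *That type I error is inflated beyond the plan.* Overriding a futility stop can only add ways to reject, and even a constant override gives 0.0478, below the stated 0.049.
- *That 15 or 21.5 extra patients should be expected.* These are ceilings. With override in a quarter of boundary-met cases, the excess at an ORR of 15% is 26 × 0.575 × 0.25 = 3.7 patients.

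**Conclusion.** The contradiction is real and should be corrected. The same Stage 1 result terminates cohort A under Section 8.1 and prompts a recommendation on whether to proceed under Sections 4.2 and 8.2.2. The 57.7% is correct for the rule in Section 8.1, but it is not assured under the other two sections. There it can lie anywhere from 57.5% down to 0%, depending on how often a recommendation to continue is made and acted on, which the documents do not say.

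The damage is limited to an unclear futility rule and avoidable enrolment after the trial's own futility criterion has been met. Across the whole range of overrides, type I error runs from 0.0446 to 0.0478 and power from 79.7% to 81.9%, so the final test is not compromised. These figures assume exact binomial responses, the printed sample sizes and the printed rejection threshold.

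**What to change.** In Sections 4.2 and 8.2.2, change the condition to: *if it does not favor the null hypothesis (4 or more responses in 22)*. The DRC's risk-benefit recommendation then applies after the boundary is passed, as the synopsis and Section 4 already provide, and 3 or fewer of 22 stops enrolment as in Section 8.1.

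If discretion at the boundary was intended, declare the futility rule non-binding in Section 8.1, align the synopsis and Section 4, and restate the operating characteristics. With the boundary always overridden, the exact values are a stopping probability of 0%, a type I error of 0.0478 and power of 81.9%.

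The first option costs one clause in each of two sections, plus a check that the DRC charter agrees. It changes neither the sample size nor the final test.
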